#### **Minimal Residual Disease (MRD) Negativity Rate**

MRD negativity rate is defined as the proportion of subjects who are MRD negative.

#### **Duration of response (DOR)**

DOR is defined as the interval from the first documentation of CR or PR to the earlier of the first documentation of definitive disease progression or death from any cause

## 3 ELIGIBILITY CRITERIA

---

### 3.1 INCLUSION CRITERIA

---

1. Prior treatment in clinical trial [UTX-TGR-304](#)
  - a. Confirmed progression by IRC on Arms B, C, or D after at least two cycles of treatment in trial UTX-TGR-304. There is no required timeframe to begin treatment on the UTX-TGR-204 protocol; however, if other therapies to treat the disease are implemented in the interim, the subject will not be eligible to enroll in the study.
  - b. Non-progressing subjects on Arm A may be eligible for enrollment when protocol UTX-TGR-304 is completed.
2. Adequate organ system function, defined as follows:
  - a. Absolute neutrophil count (ANC)  $> 750 \times 10^3/\text{mm}^3$  (0.75 K/ $\mu\text{L}$ ) / platelet count  $> 40 \times 10^3/\text{mm}^3$  (40 K/ $\mu\text{L}$ ) unless cytopenias are related to bone marrow involvement.
  - b. Total bilirubin  $\leq 1.5$  times the upper limit of normal (ULN) with the exception of Gilbert's Disease and Autoimmune Hemolytic Anemia.
  - c. Alanine aminotransferase (ALT) and aspartate aminotransferase (AST)  $\leq 2.5 \times$  ULN if no liver involvement or  $\leq 5 \times$  the ULN if known liver involvement
  - d. Calculated creatinine clearance  $> 30$  mL/min (as calculated by the modified Cockcroft-Gault formula).
3. ECOG performance status  $\leq 2$
4. Ability to swallow and retain oral medication
5. Willingness and ability to comply with trial and follow-up procedures, give written informed consent

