Inclusion Criteria	
 
Prior treatment in clinical trial UTX-TGR-304       
 
Confirmed progression by IRC from Arms B, C, or D after at least two cycles of treatment in trial UTX-TGR-304. There is no required timeframe to begin treatment on the UTX-TGR-204 protocol; however, if other therapies to treat the disease are implemented in the interim, the subject will not be eligible to enroll in the study.
 
Non-progressing subjects from Arm A may be eligible for enrollment when protocol UTX-TGR-304 is completed
 
 
 
Adequate organ system function, defined as follows:       
 
Absolute neutrophil count (ANC) <math>> 750 \times 10^3/\text{mm}^3</math> (0.75 K/<math>\mu\text{L}</math>) mL of blood / platelet count <math>> 40 \times 10^3/\text{mm}^3</math> (40 K/<math>\mu\text{L}</math>) mL of blood unless cytopenias are related to bone marrow involvement.
 
Total bilirubin <math>\leq 1.5</math> times the upper limit of normal (ULN) with the exception of Gilbert's Disease and Autoimmune Hemolytic Anemia.
 
Alanine aminotransferase (ALT) and aspartate aminotransferase (AST) <math>\leq 2.5 \times \text{ULN}</math> if no liver involvement or <math>\leq 5 \times \text{ULN}</math> if known liver involvement
 
Calculated creatinine clearance <math>> 30</math> mL/min (as calculated by the Modified Cockcroft-Gault formula (using ideal body mass [IBM])).
 
 
 
ECOG performance status <math>\leq 2</math>
 
Ability to swallow and retain oral medication
 
Willingness and ability to comply with trial and follow-up procedures, give written informed consent
 

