## 8.4 COMPLETE RESPONSE

---

To satisfy criteria for a CR, all of the following criteria must be met:

- No evidence of new disease
- ALC in peripheral blood of  $<4 \times 10^9/L$
- Regression of all target nodal masses to normal size  $\leq 1.5$  cm in the LD
- Normal spleen and liver size
- Regression to normal of all nodal non-target disease and disappearance of all detectable non-nodal, non-target disease

- Morphologically negative bone marrow defined as <30% of nucleated cells being lymphoid cells and no lymphoid nodules in a bone marrow sample that is normocellular for age
- Peripheral blood counts meeting all of the following criteria:
  - ANC  $>1.5 \times 10^9/L$  without need for exogenous growth factors (e.g., G-CSF)
  - Platelet count  $\geq 100 \times 10^9/L$  without need for exogenous growth factors
  - Hemoglobin  $\geq 110 \text{ g/L}$  (11.0 g/dL) without red blood cell transfusions or need for exogenous growth factors (e.g., erythropoietin)

Subjects who fulfill all the criteria for a CR (including bone marrow criteria) but who have a persistent anemia, thrombocytopenia, or neutropenia or a hypocellular bone marrow that is related to prior or ongoing drug toxicity (and not to CLL) will be considered as a CR with incomplete marrow recovery (CRi).

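### Inclusion criterion 2a prints the ANC entry limit as two figures that differ by a factor of 1000, in both Section 3.1 and the Synopsis

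*Combined protocol and SAP*

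**What the plan says.** Item 2 of Section 3.1 lists haematology and chemistry limits under "Adequate organ system function, defined as follows". Sub-item 2a begins "Absolute neutrophil count (ANC") and then, in the document's typesetting code, gives the limit as "750 \times 10^3/\text{mm}^3$ (0.75 K" per µL. The platelet limit follows in the same line: above 40 x 10^3/mm3, with 40 K/µL in brackets. Both limits carry one exception, "unless cytopenias are related to bone marrow involvement".

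The Synopsis prints the same pair of ANC figures with an added volume term: "750 \times 10^3/\text{mm}^3 (0.75 K/ \mu\text{L} ) mL of blood". The same added term follows the platelet limit there. Section 3.1 does not have it.

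Section 4.2 enrols subjects who are eligible and have consented, and refers to a Study Manual for the procedure. Section 9.3 removes subjects with a major protocol deviation from the Per-Protocol population and leaves the criteria for such deviations to be documented before database lock.

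**The concern.** A bracketed figure after a limit is normally the same limit in another unit. Here it is not. The line therefore carries two different minimum neutrophil counts, and nothing in it says which one governs.

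This is an operative number and not background text. It helps decide who enters the study, and it is what a monitor would hold a screening result against when checking protocol compliance under Section 11.1. If the limit has two values, a subject whose count lies between them meets one printed figure and fails the other. The protocol then offers no rule for calling that subject eligible or deviant.

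**Working it through.** **Inputs.** ANC limit: 750 x 10^3/mm3 and 0.75 K/µL (Section 3.1 item 2a; same figures in the Synopsis). Platelet limit: 40 x 10^3/mm3 and 40 K/µL (same item). ANC needed for complete response: above 1.5 x 10^9/L (Section 8.4). Conversions: 1 mm3 = 1 µL; 1 K = 1,000 cells; 1 L = 10^6 µL.

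**1. Do the two ANC figures agree?**
- First figure: 750 x 10^3/mm3 = 750,000/µL = 750 K/µL = 750 x 10^9/L.
- Bracketed figure: 0.75 K/µL = 0.75 x 1,000 = 750/µL = 0.75 x 10^9/L.
- Ratio: 750,000 / 750 = 1000. The bracketed figure is not reproduced from the first.

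**2. Control on the notation: platelets in the same line.**
- 40 x 10^3/mm3 = 40,000/µL; 40 K/µL = 40,000/µL; ratio 1.
- The notation is therefore used correctly for platelets, and no special convention explains the ANC mismatch.

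**3. Scale check within the protocol.** Section 8.4 asks for ANC "1.5 \times 10^9/L$ without need for exogenous growth factors", that is, above 1,500/µL.
- First figure: 750,000 / 1,500 = 500 times that level.
- Bracketed figure: 750 / 1,500 = 0.5 times that level.

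**4. Does the extra volume term in the Synopsis rescue the line?** Suppose mL were the intended denominator.
- ANC: 750 x 10^3 per mL = 750,000 / 1,000 = 750/µL, which would match the bracketed ANC figure.
- Platelets: 40 K per mL = 40,000 / 1,000 = 40/µL, which would put the platelet limit out by 1000 against its own bracket.
- Applied to the bracketed ANC figure itself, 0.75 K per mL = 0.75/µL.

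No single reading of the added term makes both limits consistent, and Section 3.1 lacks the term altogether.

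**5. Is it settled elsewhere?** No other current section states an ANC entry limit. The amendment history records that units were added to this item and that 2a was later clarified for marrow-related cytopenias, but it gives no value.

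**The case against.** The strongest reply is that the error exposes itself. A minimum set at 500 times the protocol's own complete-response level could not plausibly be applied, and the other figure stands beside it in the same line. The usual danger of a contradictory threshold is two workable readings under which sites enrol different patients, and that is unlikely here. This stands, and it limits the severity.

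A reader might infer that, taken literally, no subject qualifies, or that every enrolled subject is a protocol deviation. The documents do not support that. Both conclusions require a site to adopt the first figure and disregard the one in brackets, and nothing suggests that any site would.

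A reader might also infer that the error is built into an electronic eligibility check. The documents describe no such check, and the Study Manual is not among them, so whether the error reached any operational system is unknown.

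It can further be said that the planned analysis hardly depends on this item. The study has no powered sample size and no formal hypothesis test (Sections 9.1 and 9.2). Section 9.3 does not define the ITT or Safety populations by it, and the Per-Protocol analyses are supportive and optional. This also stands: no endpoint or estimate is shown to change.

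What the reply does not remove is the contradiction. The marrow-involvement exception does not help either, because it excuses subjects with a particular kind of cytopenia and does not say which number defines the limit for everyone else.

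**Conclusion.** Wrong as written; low-to-moderate severity. The mismatch is exact at 1000-fold and rests only on unit conversion. A text-extraction fault is unlikely, because two separately formatted places carry the same digits and exponent and the neighbouring platelet figure is intact.

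The practical consequence is narrow. An ANC eligibility deviation cannot be judged cleanly against the printed text, and through that the make-up of the Per-Protocol set may be affected if such deviations are classed as major. The expectation that sites would recognise a unit error is a judgement and not something the documents state. The scale check shows that something is wrong in the line; it does not establish which value the sponsor intended, and this review takes no position on that.

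**What to change.** The sponsor should decide the intended ANC limit and reconcile the two figures, either by making both notations agree, as the two platelet notations already do, or by printing only one. The wording should be identical in Section 3.1 item 2a and in Synopsis item 2a, and the added mL of blood should be deleted from both limits in the Synopsis. It would be sensible to confirm that the Study Manual and any eligibility form carry the same value, although the documents do not show that they are affected.

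The cost is a one-line correction in two places at the next amendment. If the sponsor is confirming the limit already intended, nothing changes in design, sample size or analysis.

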### 3.2 EXCLUSION CRITERIA

---

1. Prior treatment with obinutuzumab + chlorambucil (Arm B subjects) or ublituximab (Arm C subjects) within 7 days of Cycle 1/Day 1
2. Subjects refractory to (progressing on) UTX-TGR-304 Treatment Arm A (ublituximab + TGR-1202)
3. Known histological transformation from CLL to an aggressive lymphoma (i.e. Richter's transformation)
4. Evidence of chronic active Hepatitis B defined as Hepatitis B surface antigen positive or Hepatitis B DNA positive by PCR (HBV, NOT including subjects with prior hepatitis B vaccination who are Hepatitis B surface antibody positive only;) or chronic active Hepatitis C infection (HCV) defined as Hepatitis C RNA positive by PCR, cytomegalovirus (CMV) DNA positive by PCR, or known history of HIV. If HBc antibody, HCV antibody or CMV IgG and/or IgM antibody is positive the subject must be evaluated for the presence of HBV, HCV, or CMV by PCR - See [Appendix D](#).
5. Evidence of ongoing systemic bacterial, fungal or viral infection, except localized fungal infections of skin or nails. NOTE: Subjects may be receiving prophylactic antiviral or antibacterial therapies at investigator discretion. Use of anti-pneumocystis pneumonia prophylaxis is required prior to Cycle 1/Day 1 and for the first 2 cycles. After Cycle 2, is per investigator discretion.
6. Woman who are pregnant or lactating.
7. Live virus vaccines four (4) weeks prior to or during ublituximab therapy.

## 4 STUDY DESIGN

---

### 4.1 OVERVIEW OF STUDY DESIGN

---

This Companion Study is intended for subjects who previously enrolled to the parent trial [UTX-TGR-304](#). Subjects from Treatment Arms B, C, and D with disease progression confirmed by the independent review committee (IRC), may be enrolled into this Companion Study. At the end of the UTX-TGR-304 study, non-progressed subjects from Treatment Arm A may also be enrolled to this Companion Study. Subjects from Treatment Arms B, C, and D may start treatment with ublituximab + TGR-1202, while subjects entering the Companion Study from Treatment Arm A may continue their treatment as specified by this protocol. All subjects enrolled to the Companion Study should receive ublituximab in combination with TGR-1202 (at the same dose and schedule as the Treatment Arm A in UTX-TGR-304) until they show disease progression, are unable to continue treatment for any reason such as lack of tolerability, or until the treatment is commercially available.

During the study period, all subjects will be evaluated for response by CT and/or MRI. Evaluations are to be obtained at approximately cycles 3, 6 and 12. Following cycle 12, evaluations should occur at least every 12 cycles unless clinically indicated more frequently. Subjects should remain on study treatment until the occurrence of definitive disease progression, unacceptable toxicity, or withdrawal from the study due to investigator decision or other reasons. Subjects who discontinue from study treatment (either for toxicity or physician choice) and have not progressed should continue to be followed for progression per institutional standard of care and reported in eCRF. Date of progression, beginning of new treatment, and/or death should be entered in the eCRF.

### 4.2 REGISTRATION

---

Subjects who are eligible and who have signed an informed consent will be enrolled. Please see Study Manual for enrollment procedures.

### 4.3 STUDY SITES

---

Only sites participating in UTX-TGR-304 will be included in this study.

### 4.4 DISCONTINUATION FROM STUDY TREATMENT

---

Subjects will be discontinued from study treatment for any of the following reasons:

- Disease progression
- Intolerable toxicity related to study drug
- Subject requests to withdraw consent or discontinue treatment
- Pregnancy
- Inability of the subject to comply with study requirements
- Conditions requiring therapeutic intervention not permitted by the protocol
- Non-compliance/lost to follow-up
- Investigator discretion
- Discontinuation of the study by the Sponsor

Subjects who discontinue from study treatment (for reasons other than progressive disease) should continue to be followed for progression.

Subjects who discontinue all study treatment but remain on study for disease progression assessment will have an End of Treatment (EOT) visit and will continue to be followed for adverse events (treatment-related AEs and disease-related AEs), disease progression and other protocol required procedures (see [Section 5, Table 2](#) for EOT and follow up assessment schedule). All new treatment-related AEs occurring within 30 calendar days from treatment discontinuation must be reported and followed until resolution, unless, in the opinion of the investigator, these events are not likely to improve because of the underlying disease. In this case the investigators must record the reason for not conducting the 30-day safety evaluation in the subject's medical records and as a comment on the electronic Case Report Form (eCRF).

All subjects who have CTCAE Grade 3 or 4 laboratory abnormalities at the time of withdrawal should be followed until the laboratory values have returned to Grade 1 or 2, unless in the opinion of the investigator, it is not likely that these values are to improve because of the underlying disease. In this case, the investigator must record his or her reasoning for making this decision in the subject's medical records and as a comment on the eCRF.

Subjects who discontinue from the study will have an End of Study visit (EOS - see [Section 5, Table 2](#))

No formal futility analysis of efficacy or safety will be conducted in this study, however if [Study 304](#) is closed for futility for either safety or efficacy reasons, then this Study UTX-TGR-204 will also be terminated.

## 5 STUDY ASSESSMENTS AND TREATMENT SCHEDULE

The table below lists all of the required assessments that should be performed at each study visit.

TABLE 1: STUDY ASSESSMENT AND TREATMENT SCHEDULE

Cycle (C) = 28 days	Screening 	Cycle 1 				Maintenance 		Cycles 15+ 	End of study	
						Cycles 2 - 6	Cycle 9 & 12			
Procedure \ Days (D)	-28-0	D 1	D 2	D 8	D 15	Day 1	Day 1	Q 3 cycles		
Medical History	X									
Rai Staging	X									
ECOG performance status	X	X			X	X	X	X	X	
Physical examination	X	X		X	X	X	X	X	X	
Vital signs (pulse, BP, temp)	X	X		X	X	X	X	X	X	
BM aspirate/biopsy 	X									
Serum Pregnancy Test 	X									
Urine Pregnancy Test 						X	X	X	X	
Hematology 	X 	X	X	X	X	X	X	X	X	
Serum Chemistry	X 	X		X	X	X	X	X	X	
FISH Panel 	X									
Tumor evaluation 	X	Evaluations are to be obtained during cycles 3, 6 & 12. Following cycle 12, evaluations should occur at least every 12 cycles								
Serology: HCV, HBV, CMV 	X									
CMV Surveillance						X 	X	X 		
MRD 						For subjects in PR or CR beginning at the Cycle 6 response assessment				
Ublituximab 		X	X 	X  5	X 	X	X	Q3 months		
Umbralisib (TGR-1202) Dose		Days 1 - 28 (Daily)								
Adverse events (CTC v4.0)		Throughout the study								X 
Concomitant Medication		Throughout the study								X

 Tests that have already been completed as part of the requirements for UTX-TGR-304 may be used to evaluate eligibility for this companion study

 Treatment Administration +/- 1 day window. Physical Exam, Vital Signs, ECOG PS, Hematology and Serum Chemistry visit days have - 1 day window

 Treatment Administration +/- 3 day window Cycles 2-6. Physical Exam, Vital Signs, ECOG PS, Hematology and Serum Chemistry visit days have a - 3 day window during Cycles 2 through 6. Treatment Administration +/- 7 day window after Cycle 6. Physical Exam, Vital Signs, ECOG PS, Hematology and Serum Chemistry visit days have a - 7 day window for all cycles after cycle 6

 Treatment Administration +/- 7 day window. Physical Exam, Vital Signs, ECOG PS, Hematology and Serum Chemistry visit days have a - 7 day window for all cycles after cycle 6

 Unilateral bone marrow aspirate and/or biopsy performed at investigator discretion in subjects for whom assessment of extent of CLL involvement and bone marrow cellularity is important. In addition, a post-baseline bone marrow biopsy should be completed to confirm potential CR by radiological assessment.

 For women of child bearing potential, completed within 3 days of Cycle 1 Day 1.

 For women of child bearing potential, completed within 3 days of visit

 Must be obtained prior to ublituximab administration if on day of infusion.

 Must be done within 14 days of cycle 1 day 1

 For del(13q), del(11q), del(17p), and (12) trisomy, t(11:14)

 Scans should be completed approximately 45 days prior to Day 1 of Cycle 1. Radiology assessment should include CT or MRI imaging of chest, abdomen, and pelvis.

 Serum virology to include HBsAg, HbC antibody, HCV antibody and CMV IgG and IgM. If HbC antibody, HCV antibody or CMV IgM is positive, subjects must be evaluated for the presence of active HBV, HCV or CMV by PCR

 Q3 months CMV screening by PCR for all subjects.

 Peripheral blood sample may be analyzed by local lab. For subjects MRD negative by peripheral blood, a bone marrow should be completed to confirm MRD negativity. If a bone marrow is not completed, another peripheral blood sample should be collected to confirm the MRD negativity at least 12 weeks later. MRD should continue to be evaluated for subjects with PR/CR at response assessment intervals until 2 consecutive peripheral blood MRD negative results, or 1 negative peripheral blood MRD and 1 negative bone marrow MRD are observed.

 Subjects who received ublituximab on UNITY-CLL trial (Arm C), will not receive split dosing on Day 1 and 2 of cycle 1. Subjects should receive full dose on Cycle 1, Day 1 and will not receive Day 8, and 15 during Cycle 1.

 If clinically significant adverse event or abnormal result is observed that is not resolved by the end-of treatment visit, continue to monitor and record up through 30 days after study drug discontinuation.

TABLE 2: FOLLOW UP ASSESSMENTS SCHEDULE

Procedures 	Off Protocol Treatment for Non-PD (AE, investigator decision, etc.) NOT Receiving Non-Protocol Treatment	Off Protocol Treatment for Non-PD (AE, investigator decision, etc.) Receiving Non-Protocol Treatment	Off Protocol Treatment for PD
ECOG Performance Status	X		
Physical Exam	X		
Vital Signs	X		
Hematology	X		
Chemistry	X		
MRD	X		
Con Meds	To be followed for 30 days after last day of study drug(s)		
AE Evaluation	To be followed for 30 days after last day of study drug(s)		
Tumor Evaluations 	X		
EOT Page	X	X	X
Post Treatment Visits	X		
EOS Visit 		X	X

 PFS off treatment should be assessed per institutional standard of care.

 CT or MRI imaging of the Neck, Chest, Abdomen, and Pelvis should be completed per institutional standard of care. There is no central radiology review for this study.

 EOS visit should be documented in the EDC once subject has PD and/or starts non-protocol therapy.

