Exclusion Criteria	
 
Prior treatment with obinutuzumab + chlorambucil (Arm B subjects) or ublituximab (Arm C subjects) within 7 days of Cycle 1/Day 1.
 
Subjects refractory to (progressing on) UTX-TGR-304 Treatment Arm A (ublituximab + TGR-1202).
 
Known histological transformation from CLL to an aggressive lymphoma (i.e. Richter's transformation).
 
Evidence of chronic active Hepatitis B defined as Hepatitis B surface antigen positive or Hepatitis B DNA positive by PCR (HBV, NOT including subjects with prior hepatitis B vaccination who are Hepatitis B surface antibody positive only;) or chronic active Hepatitis C infection (HCV) defined as Hepatitis C RNA positive by PCR, cytomegalovirus (CMV) DNA positive by PCR, or known history of HIV. If HBc antibody, HCV antibody or CMV IgG and/or IgM antibody is positive the subject must be evaluated for the presence of HBV, HCV, or CMV by PCR - See Appendix D.
 

	
 
5. Evidence of ongoing systemic bacterial, fungal or viral infection, except localized fungal infections of skin or nails. NOTE: Subjects may be receiving prophylactic antiviral or antibacterial therapies at investigator discretion. Use of anti-pneumocystis pneumonia prophylaxis is required prior to Cycle 1/Day 1 and for the first 2 cycles. After cycle 2, is per investigator discretion.
 
6. Woman who are pregnant or lactating.
 
7. Live virus vaccines four (4) weeks prior to or during ublituximab therapy.
 

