### 5.1.1 LABORATORY EVALUATIONS (LOCAL LAB)

1. Hematologic profile and serum chemistry to include:

Serum Chemistry		
Albumin	Creatinine	SGOT [AST]
Alkaline phosphatase	Glucose	SGPT [ALT]
Bicarbonate/ CO 2	LDH	Sodium
BUN	Magnesium	Total bilirubin
Calcium	Phosphorus	Total Protein
Chloride	Potassium	Uric acid
Hematologic Profile		
Hematocrit	Neutrophils	Platelet count
Hemoglobin	Lymphocytes	
Erythrocyte count	Monocytes	
Absolute neutrophil count	Eosinophils	
Absolute leukocyte count	Basophils	

2. Serum and urine pregnancy tests
3. Baseline bone marrow aspirate/biopsy (if applicable)
4. CLL FISH Panel
5. MRD for subjects in CR or PR beginning at Cycle 6 response assessment
6. Serum Virology to include HBsAG, HBc antibody, HCV antibody, and CMV IgG and IgM. If HBc antibody, HCV antibody or CMV IgM are positive the subject must be evaluated for the presence of active HBV, HCV or CMV by PCR - See [Appendix D](#). For all subjects approximately every 3 months CMV screening by PCR. CMV surveillance will discontinue 30 days after last dose of umbralisib, or as otherwise clinically indicated per investigator discretion.

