Grade 1 & 2	Withhold umbralisib as warranted, provide supportive care and hold until complete resolution. Resume umbralisib at one dose lower.  If recurrence after re-challenge, discontinue umbralisib.
Grade $\geq 3$	Discontinue umbralisib and intervene as warranted.
*For sinopulmonary infections clearly not related to immune-mediated pneumonitis, umbralisib may be continued at investigator's discretion. While pneumonitis has been minimal with umbralisib, it is a reported adverse event associated with other PI3K delta inhibitors. Use of anti-pneumocystis and anti-herpetic viral prophylaxis is required at start of therapy.	
Liver Toxicity (ALT/SGPT, AST/SGOT, Bilirubin, Alkaline Phosphatase)	

Grade 1	
 
Maintain current dose
 
Assess Concomitant Medications and Risk Factors*
 
Monitor Labs every 1-2 weeks
 

Grade 2	
 
Maintain current dose
 
Assess Concomitant Medications and Risk Factors*
 
Begin supportive care (40-60 mg prednisone orally per day or equivalent)**
 
Monitor labs at least weekly until Grade 1
 
Once resolved to Grade <math>\leq 1</math>, taper prednisone by 10 mg per week until off.                             
 
If liver toxicity recurs to Grade 2 once off steroids, re-initiate steroids with 10 mg per week taper until off.
 
Consider withholding umbralisib. If delay is greater than 2 cycles notify TG Therapeutics prior to re-initiating.
 
 
 

Grade $\geq 3$	
 
Hold Umbralisib. If delay is greater than 2 cycles notify TG Therapeutics prior to re-initiating.
 
Assess Concomitant Medications and Risk Factors*
 
Begin/continue supportive care (40-60 mg prednisone orally per day or equivalent)**
 
Monitor labs at least weekly until Grade 1
 
Once resolved to Grade <math>\leq 1</math>, taper prednisone by 10 mg per week until off
 
Resume -1 dose level when Grade <math>\leq 1</math>
 

* Assess for disorders of lipids and glucose, thyroid disorders, alcohol use, viral infections, etc.
 
**Supportive Care – Aggressive management of lipid, glucose, other metabolic disorders, viral infections, etc. Important: Before initiating steroids, check for viral hepatitis or CMV infection.
	
Diarrhea and/or Colitis	

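### The screening schedule and laboratory section require CMV PCR only for positive IgM, while Exclusion 4 requires it for positive IgG and/or IgM

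*Combined protocol and SAP*

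**What the plan says.** Exclusion 4 bars subjects who are CMV DNA positive by PCR and states when that PCR must be done. In Section 3.2 the rule is "If HBc antibody, HCV antibody or CMV IgG and/or IgM antibody is positive the subject must be evaluated". The Synopsis carries the same rule: "CMV IgG and/or IgM antibody is positive the subject must be evaluated for the presence of HBV, HCV, or CMV by PCR".

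Two other current sections state the trigger differently. Table 1 footnote 12 puts both CMV IgG and IgM in the screening panel, then conditions PCR as follows: "If HbC antibody, HCV antibody or CMV IgM is positive". Section 5.1.1 item 6 also collects both antibodies and then says: "If HBc antibody, HCV antibody or CMV IgM are positive the subject must be evaluated". Neither attaches any action to a positive IgG.

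Section 5 introduces Table 1 with the words "The table below lists all of the required assessments that should be performed at each study visit". Footnote 13 adds surveillance during treatment: "Q3 months CMV screening by PCR for all subjects". In Table 1 the CMV Surveillance row is blank at Screening and Cycle 1, and its first mark is in the Cycles 2–6 column.

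**The concern.** PCR is the deciding test for a safety exclusion, so the rule for ordering it should be the same wherever a site might look. For an IgG-positive, IgM-negative subject it is not: the eligibility lists make PCR mandatory, and the schedule and laboratory section do not call for it. Because Section 5 presents Table 1 as the complete list of required assessments, a site could reasonably order screening tests from it. That site would hold a positive IgG result with no instruction there to follow it up.

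At stake is the start of combination treatment in a subject whose CMV DNA status is unknown and who might have been excluded. The enrolment would follow the schedule yet breach Exclusion 4.

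**Working it through.** The plan gives no figure to reproduce on this point. The check compares the texts and then works out the timing.

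**The four statements of the trigger**

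| Place | CMV antibodies named | PCR required when |
|---|---|---|
| Synopsis, Exclusion 4 | IgG and IgM | IgG and/or IgM positive |
| Section 3.2, Exclusion 4 | IgG and IgM | IgG and/or IgM positive |
| Table 1 footnote 12 | IgG and IgM | IgM positive |
| Section 5.1.1 item 6 | IgG and IgM | IgM positive |

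The possible serology results are then:

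- IgM positive, with any IgG result: all four places require PCR.
- Both negative: none requires it.
- IgG positive, IgM negative: the two eligibility lists require it and the other two places do not.

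The mismatch is confined to this last group. The hepatitis B core antibody and HCV antibody triggers agree in all four places.

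**When a missed subject would first be tested (Arms B, C and D)**

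Inputs: a cycle is 28 days (Table 1); dosing is as in Section 6.1; the surveillance marks are as in Table 1. Assumptions: the PCR is drawn before that day's dose, and visit windows are ignored.

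- Earliest reading, Cycle 2 Day 1: 1 × 28 = 28 days after the first dose.
- Three months counted as three cycles from Cycle 1 Day 1, so Cycle 4 Day 1: 3 × 28 = 84 days after the first dose.

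**Planned dosing before that test**

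- Umbralisib 800 mg daily: 28 or 84 doses.
- Ublituximab, Arms B and D, Cycle 1: 150 + 750 + 900 + 900 = 2,700 mg. Adding Day 1 of Cycles 2 and 3: 2,700 + 2 × 900 = 4,500 mg.
- Ublituximab, Arm C, Cycle 1: 900 mg. Adding Day 1 of Cycles 2 and 3: 900 + 2 × 900 = 2,700 mg.

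**The case against.** The strongest reply is that the rules do not conflict. Footnote 12 and Section 5.1.1 say when PCR is mandatory; they do not say it is unnecessary in IgG-only subjects. A site applying Exclusion 4 satisfies every section, and Section 4.2 limits entry: "Subjects who are eligible and who have signed an informed consent will be enrolled". This is correct, and it is why the consequence is only that a subject could be missed. It does not remove the defect. No order of precedence between the sections is stated, and eligibility on this criterion can be judged only if the PCR was ordered.

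Other provisions narrow the gap without closing it:

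- **Three-monthly PCR.** This is surveillance on treatment, with no mark before Cycle 2, so it cannot decide an entry exclusion.
- **Liver toxicity note in Table 4 (Section 6.4.2).** It says "Before initiating steroids, check for viral hepatitis or CMV infection", but it applies only once liver toxicity is being managed.
- **Exclusion 5.** It bars ongoing systemic viral infection, which should catch clinically evident CMV disease. It names no test, so DNA positivity without other signs remains.
- **Table 1 footnote 1.** Tests from the parent trial may be used for eligibility, but these documents do not show that a CMV PCR was among them.
- **Antiviral prophylaxis (Section 6.2.2).** It is required through Cycle 2, but the documents do not say that it covers CMV.

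It can also be argued that the sponsor may have meant IgM only, since the Version 6.0 entry in the amendment log uses that wording. The log does not override the current eligibility text, which is the same in both places.

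One further point stands. The dose totals describe planned exposure for a hypothetical missed subject and do not measure CMV risk. They also do not mean first exposure to both drugs, because Arm C had already received ublituximab and Arm D umbralisib in the parent trial.

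**Conclusion.** The inconsistency is real and lies between current operative sections. For IgG-positive, IgM-negative subjects, Table 1 footnote 12 and Section 5.1.1 item 6 leave out a pre-dose PCR that Exclusion 4 requires, and no other provision supplies it. The delay of 28 to 84 days rests on the surveillance readings stated above. The upper figure is not a hard limit: three calendar months is about 91 days, and visit windows would move either figure.

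The number of subjects affected cannot be estimated, because the documents give no CMV serostatus, DNA positivity or site-adherence figures. The point is minor. It concerns eligibility and safety, it changes no statistical figure in the plan, and it has no demonstrated effect on the efficacy analyses. It should still be corrected, because it governs the test for a safety exclusion.

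**What to change.** In the PCR trigger of Table 1 footnote 12 and of Section 5.1.1 item 6, replace CMV IgM with CMV IgG and/or IgM. Leave Exclusion 4 unchanged in the Synopsis and Section 3.2, where the stricter trigger already stands.

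The cost is two wording edits. The only added burden falls on sites that had been ordering from the schedule, and it is the screening PCR that Exclusion 4 already requires of them. No new procedure is introduced.
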